surgery. 4 electrodes were placed 2-3 cm lateral to the incision of the patients at the 30th minute and 2, 18, 22, 42, and 46th hours after the surgery and electrical stimulation was implemented at varying frequencies of 2-100 Hz for 30 minutes, at a maximum current intensity of 12 milliamperes that would not bother the patient or create muscle contractions, with a pulse duration of 0.25 min. . (Figure 1).

Second Intervention Group: The Patient Controlled Analgesia infusion was started right after the surgery. 4 electrodes were placed at the ST25, P6, ST36, and LI4 acupuncture points of the patients at the 30th minute and 2, 18, 22, 42, and 46th hours after the surgery and electrical stimulation was implemented at varying frequencies of 2-100 Hz for 30 minutes, at a maximum current intensity of 12 milliamperes that would not bother the patient or create muscle contractions, with a pulse duration of 0.25 min. (Figure 2).

Control Group: The Patient Controlled Analgesia infusion was started right after the surgery. No intervention was performed to the patients in the control group. The data of the patients were recorded at the post-operative 30th minute and 2, 18, 22, 42, and 46th hours. The flow chart of the study is shown in Figure 3.

The TENS device used in this study was a dual channel nerve stimulator. This device had 7 preset pain programs and 3 special programs. The program and the amplitude could be set individually for each channel. The electrodes of the device were 4x4 cm in size with 4 pieces in total. The electrodes were placed 2-3 cm lateral to the incision area and at the relevant acupuncture points. The current intensity was manually set according to the patient's tolerance.

Measurements

Baseline measurements

Preoperative measurements: The patients' age, gender, height, weight, diagnosis, history of a chronic sleep disorder and ASA class data were recorded. Pulmonary functions (PEF, FVC), vital signs, respiratory rate, saturation and pain level data were also recorded.

Outcome measurements

Intraoperative measurement: All patients received general anesthesia with the same protocol. The patients were observed during the surgical procedure and data such as incision length, duration of anesthesia, duration of surgery and number of drains were recorded.

Postoperative measurements: The medical findings of all patients after the surgical procedure were recorded.

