Pain: VAS with a range of 1-10 points was used while the pain levels of all patients were evaluated. Pain levels of all patients were evaluated at rest.

Analgesic drug consumption: All patients were administered IV Contramal infusion with PCA for the first 48 hours. Dexketoprofen Trametamol vial IV and/or 50 mg. Pethidine HCl IM was used as the rescue analgesic.

Nausea severity: VAS with a range of 1-10 points was used while evaluating the nausea severity of all patients .

Vomiting: The number of times the patients vomited was recorded.

Antiemetic drug consumption: The antiemetic drug amount administered to the patients was recorded in mg.

Pulmonary function tests: The pulmonary functions of the patients were evaluated with a portable spirometer. PEF and FVC values were recorded. The measurement of respiratory functions was performed with the patient wrapping the disposable mouthpiece well with the lips during the measurement. The patient was asked to breathe deeply and exhale suddenly and quickly. This process was repeated three times and the best performance was taken as the base value.

Sample size: The software package G-power 3.1.3. was used to conduct a prior power analysis to calculate the number of participants required. Sixteen participants were required to detect an effect size of 1.4 at 80% power. The alpha level used to define significance was 0.05.

Blinding: Because the patients and data collector were aware they were implementation electrical stimulation or not, there was no blinding to the study.

Data collection: Data collection was started on the day before the patients underwent surgery and finished on the 2nd day after surgery.

Preoperative data collection: The characteristics of the patients and ASA classifications, vital signs and respiratory functions were evaluated one day prior to the surgery.

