Postoperative data collection: The medical information of the patients was recorded within the initial 48 hours after the surgery. Vital signs, respiratory functions, pain levels, nausea severity, vomiting status, dizziness status, analgesic and antiemetic drug consumption of all patients included in the study were recorded. Vital signs and pain levels of the patients in the control group were evaluated at the post-operative 30th min. and 2,18,22,42, and 46th hours. Vital findings and pain levels of the patients who were included in the intervention groups before and 30 minutes after the implementation were evaluated. All evaluations of the patients were performed during bed rest. Nausea levels, vomiting status and dizziness status of the patients were evaluated at the periods of 0-6, 6-24, and 24-48 hours. Analgesic and antiemetic drug consumption of the patients was

evaluated at the periods of 0-24 and 24-48 hours. Respiratory function evaluations of the patients were performed at the 24th and 48th hours.

Data analysis:

The data obtained from this study were evaluated by using the Statistical Package for the Social Sciences (SPSS, Inc., Chicago, IL, USA) 22.0 software program.

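### Pain at 30 minutes is a common pre-stimulation baseline in all three arms, but the plan neither names it as one nor adjusts for it when comparing arms

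*Combined protocol and SAP*

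**What the plan says.** The interventions section gives both active arms the same schedule. Electrodes are placed "at the 30th minute and 2, 18, 22, 42, and 46th hours after the surgery and electrical stimulation was implemented", and each session lasts half an hour. No arm-specific procedure is described before the 30th minute.

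Postoperative data collection sets the pain readings. Control patients are read once at each time: vital signs and pain "in the control group were evaluated at the post-operative 30th min. and 2,18,22,42, and 46th hours". Active patients are read twice per session: "Vital findings and pain levels of the patients who were included in the intervention groups before and 30 minutes after the implementation were evaluated".

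The only pain value under Baseline measurements is preoperative: "Pulmonary functions (PEF, FVC), vital signs, respiratory rate, saturation and pain level data were also recorded". Preoperative data collection places some assessments on the day before surgery ("vital signs and respiratory functions were evaluated one day prior to the surgery"), but its list does not name pain.

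Data analysis compares the three groups by one-way ANOVA or Kruskal-Wallis, with no covariate and no change score. Before and after values are compared only within a group, by paired t or Wilcoxon test. The Blinding paragraph says that neither patients nor the data collector are blinded. The Randomization section does not say when an allocation is disclosed.

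**The concern.** Pain is a primary outcome with no stated primary time. Control readings are listed at six times without distinction, so a reader could take all six as outcome times and run the three-group test at each. The first of them differs in kind from the rest: in control, and in the active arms' pre-session reading, it is taken before anyone has been stimulated.

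Two things are at stake. First, a between-arm difference at 30 minutes could be presented as a treatment effect when the comparison cannot support that. Second, a post-incision measure of each patient's pain, already collected in every arm, does not enter the randomised comparison. The preoperative value predates the incision, in patients from whom chronic pain has been excluded, so it can say little about how painful the operation is for a given patient.

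**Working it through.** **1. Readings at the first session**

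| | Control | Active arms |
|---|---|---|
| First reading | 30 min | about 30 min, before stimulation |
| Reading after first session | none scheduled | about 60 or 90 min |
| Next scheduled time | 2 h | 2 h, before the second session |

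The plan does not say whether the half hour before the post-session reading runs from the start or the end of the session. From the start, it falls at 30 + 30 = 60 min. From the end of a 30-minute session, it falls at 30 + 30 + 30 = 90 min.

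**2. What a between-arm contrast at the first time can show**

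- Pre-session reading against control: 30 min against 30 min, with no arm yet stimulated. The true stimulation effect is zero, and a difference reflects chance or a reaction to knowing the arm.
- Post-session reading against control: 60 or 90 min against 30 min. Stimulation can act, but its effect is mixed with 30 to 60 minutes of extra recovery and patient-controlled analgesia. Control's next reading, at 120 min, is also 120 − 90 = 30 to 120 − 60 = 60 minutes away.

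The plan does not say which active-arm reading is set against control, at this time or at any of the other five.

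**3. The plan's own sample size**

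The Sample size paragraph gives 16 participants for an effect size of 1.4, 80% power and alpha 0.05. It does not state sidedness, the type of effect size, or whether 16 is per arm or in total. Reading 1.4 as a standardised difference between two means:

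- one-sided two-sample t test: 7.10, so 8 per arm and 16 in two arms (power 0.845), which matches;
- two-sided t test: 9.08, so 10 per arm and 20 in two arms, which does not match;
- two-sided normal approximation: 8.01, so 9 per arm and 18 in two arms, which is close.

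The point does not depend on this figure. It does show why both 8 and 16 per arm are worth considering.

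**4. Gain from adjustment**

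With correlation r between the 30-minute reading and a later one, residual variance is 1 − r², the equivalent sample-size factor is 1/(1 − r²), and the effective standardised difference is 1.4/√(1 − r²). The values of r are assumptions. Power is for a two-sided t test at 0.05.

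| r | 1 − r² | 1/(1 − r²) | Effective difference | Power, 8 per arm | Power, 16 per arm |
|---|---|---|---|---|---|
| 0 | 1 | 1 | 1.40 | 0.740 | 0.969 |
| 0.3 | 0.91 | 1.10 | 1.47 | 0.779 | 0.980 |
| 0.5 | 0.75 | 1.33 | 1.62 | 0.852 | 0.993 |
| 0.7 | 0.51 | 1.96 | 1.96 | 0.954 | above 0.99 |

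These powers ignore the degree of freedom spent on the covariate, so they are slightly optimistic, more so at 8 per arm.

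**The case against.** The strongest reply is that an unadjusted ANOVA or Kruskal-Wallis test is valid in a randomised trial. Its error rate already allows for chance imbalance in early pain, so adjustment is a choice about precision. That stands. The gain also rests on a correlation that the documents do not give: the reading comes soon after general anaesthesia and would have to predict pain as late as 46 h. At r = 0.1 the residual variance is 1 − 0.01 = 0.99, so the gain is about 1%. If 16 means per arm, unadjusted power is already 0.969 and there is little to add.

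Some stronger readings are tempting but are not supported:

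- A reader might infer that the first session can show no effect at all. That holds only if the pre-session reading is compared with control; the active arms also have a post-session reading, which follows stimulation.
- A reader might infer that the first pre-session reading goes unused. It enters the within-group paired test; it is missing only from the between-arm comparison.
- A reader might infer that the plan declares the 30-minute reading an outcome. Postoperative data collection lists times and assigns no roles, and a test at 30 minutes could be meant as a check of comparability.
- A reader might infer that baseline pain is taken the day before surgery. That is plausible, but the day-before list does not name pain; the text supports only preoperative.

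Silence on when allocation is disclosed shows a gap in the plan, not that harm occurred.

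**Conclusion.** The concern holds as a point about efficiency and clarity; it does not make the later comparisons invalid. All three arms have a time-matched reading after the incision and before stimulation, which the plan neither labels as a baseline nor uses in the randomised comparison. At the first time point, neither possible between-arm contrast is a sound test of stimulation: one precedes treatment and the other is not time-matched.

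At assumed correlations of 0.3 to 0.7, the gain from adjustment is equivalent to 1.10 to 1.96 times as many patients. It is smaller if the correlation is lower. The gain in power is material at 8 per arm and small at 16 per arm. These power figures also assume that 1.4 is a standardised difference between two means.

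**What to change.** In Measurements, Postoperative data collection and Data analysis:

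1. Name the 30-minute reading (before the first session in the active arms, at the same minute in control) as the post-operative pain baseline. Do not report a between-arm test at that time as a treatment effect.
2. Compare the arms on pain from 2 h onward with this reading as a covariate, by ANCOVA or a rank-based equivalent. State in advance whether the pre-session or the post-session active reading is set against the single control reading, and note that a post-session reading is not time-matched to control. Keep the first session's post-session reading as descriptive or within-group only.
3. Because the trial is unblinded, where workable disclose each allocation only after the 30-minute reading is recorded, so that knowledge of the arm cannot affect the covariate. This looks feasible, since no arm-specific step is described before that minute.

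The reading is already scheduled in every arm, so no new measurement is needed. The cost is protocol and analysis wording, one fewer between-arm time point, no between-arm use of the first post-session reading, and allocation opened at the bedside.

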**The Effects of Two Different Electrical Stimulation Methods on the Pain Intensity of
the Patients Who Had Undergone Abdominal Surgery With a Midline Incision:
Randomized Controlled Clinical Trial**

[name]

[name], Professor

Document Date: May 1, 2015

The effects of two different electrical stimulation methods on the pain intensity of the patients who had undergone abdominal surgery with a midline incision: Randomized Controlled Clinical Trial

**[name]
[name]**

This study was conducted as a randomized controlled trial. The primary outcome measures were the effects of TENS and TAES on pain and analgesic drug consumption in patients who had undergone abdominal surgery with a midline incision. Secondary outcome measures were the effects of TENS and TAES use on respiratory functions, vital signs, nausea and vomiting status, dizziness, antiemetic drug consumption, and saturation

Study setting

This study was conducted at the Department of General Surgery of the Gülhane Training and Research Hospital in Ankara, Turkey between May 2015 and November 2016.

Participants

The population consisted of General Surgery patients who underwent planned abdominal surgery with a midline incision between May 2015 and November 2016. The study sample comprised patients who underwent abdominal surgery with a midline incision due to problems related to colorectal cancer and stomach cancer. The principal investigator evaluated patients awaiting abdominal surgery with a midline incision in the hospital room the day before the surgery to ensure that the patients qualified for the study in accordance with the eligibility criteria.

Inclusion criteria

Patients who had an American Society of Anesthesiologists (ASA) score of I-II, were aged over 18 years, who could read and write Turkish, who were scheduled to undergo elective abdominal surgery with a midline incision for a diagnosis of stomach or colorectal cancer, and without any impairment of vision, hearing or speech were included in the study.

Exclusion criteria

Patients who had a pacemaker, whose skin integrity around the incision was degraded, had a cognitive disorder, had a history of chronic pain, or were suffering from neurological, renal, cardiac or pulmonary disorders that could affect the test results, and patients with an opioid addiction, those who had previously undergone electrical stimulation treatment, morbidly obese subjects and patients using

psychoactive drugs were excluded.

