After the data were transferred to the SPSS database, error controls were performed. Their compliance with a normal distribution was evaluated with Kolmogorov Smirnov test. The data determined were mean \pm standard deviation ($X \pm SS$), median and minimum-maximum (min-max) for the variables determined by the measurement and number (n) and percent (%) for the variables determined by counting. Since the variables determined by counting did not comply with a normal distribution, the difference between the three groups was evaluated by the Chi square test. The one-way ANOVA test was used to investigate the difference between the three groups regarding the measured values for values complying with normal distribution and the Kruskal-Wallis test was used for the values that did not comply with a normal distribution. The Bonferroni correction was implemented to determine the source of the difference in group comparisons. The Mann-Whitney U test was used to investigate the difference between two groups of variables. A p value <0.05 was accepted as statistically significant. The Paired Sample T Test was used for values complying with a normal distribution and the Wilcoxon Test was used for values not complying with a normal distribution when comparing the values of patients in the same group before and after the implementation.

Ethical consideration: Written permission and approval was obtained from the Gülhane Military Medical Academy's Head of Clinical Studies Ethics Committee before the study started. Physicians and nurses working at the Gülhane Military Medical Academy, General Surgery Clinic, Post-Operative Care Unit and Post-Anesthesia Care Unit within the Anesthesiology and Reanimation Clinic were informed of the study and verbal approval was obtained.

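### Pain and vital signs have no control reading at the clock time of the post-session reading, so the session effect against control cannot be estimated free of elapsed time

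*Combined protocol and SAP*

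**What the plan says.** All places are in the combined protocol and SAP.

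- **Outcome.** The opening description states: "The primary outcome measures were the effects of TENS and TAES on pain and analgesic drug consumption". Vital signs are secondary.
- **Control readings.** Under Postoperative data collection: "Vital signs and pain levels of the patients in the control group were evaluated at the post-operative 30th min", followed by 2, 18, 22, 42 and 46 hours. The Control Group paragraph of The interventions gives the same list: "The data of the patients were recorded at the post-operative 30th minute and 2, 18, 22, 42, and 46th hours".
- **Stimulated readings.** Under Postoperative data collection: "Vital findings and pain levels of the patients who were included in the intervention groups before and 30 minutes after the implementation were evaluated".
- **Sessions.** In both intervention groups the electrodes go on at the same six times and "electrical stimulation was implemented at varying frequencies of 2-100 Hz for 30 minutes". Controls receive no sham session.
- **Analysis.** Under Data analysis: "The one-way ANOVA test was used to investigate the difference between the three groups regarding the measured values", with Kruskal-Wallis where normality fails. The paired t-test and Wilcoxon test apply "when comparing the values of patients in the same group before and after the implementation". For two-group comparisons: "The Mann-Whitney U test was used to investigate the difference between two groups of variables". None of these sentences names the reading, before or after, that represents a stimulated patient.

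The flow chart (Figure 3) is not in the text available, so this point rests on the written schedule, which two sections give identically.

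**The concern.** Stimulated patients have two readings per session and controls have one. If the after reading is compared with the control reading, the difference mixes stimulation with 30 or 60 minutes of postoperative course. If the before reading is compared, the clock times agree, but the session in question has not yet taken place.

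The within-group tests do not fill the gap. They are valid tests of change over time, but they cannot separate stimulation from natural course, patient-controlled analgesia (PCA) or rescue drugs.

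Pain is one of two primary outcomes. As written, a reader cannot tell whether the three-group pain result is a clock-matched test of carry-over or a contrast mixed with drift. The bias could go either way: falling pain would flatter the device, and rising pain would hide a benefit. The worry is greatest at 30 minutes and 2 hours, soon after the anaesthetic agents stop, and may be negligible from 18 hours on.

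**Working it through.** **1. Clock times by arm (hours after surgery)**

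| Reading | Times | Matched to a control reading |
|---|---|---|
| Control | 0.5, 2, 18, 22, 42, 46 | n/a |
| Stimulated, before | 0.5, 2, 18, 22, 42, 46 | 6 of 6 |
| Stimulated, after (30 min from session start) | 1, 2.5, 18.5, 22.5, 42.5, 46.5 | 0 of 6 |
| Stimulated, after (30 min from session end) | 1.5, 3, 19, 23, 43, 47 | 0 of 6 |

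The plan does not say whether the 30 minutes run from the start or the end of the session; the result is the same. A between-group difference in change cannot be formed either, because controls have no second reading.

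**2. What the before readings measure.** The 0.5 h reading precedes all stimulation. The others come 1, 15.5, 3.5, 19.5 and 3.5 h after the previous session ended (for example 2 − 0.5 − 0.5 = 1).

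**3. Analgesia possible between the two readings.** From the PCA settings (5 mg/h infusion, 20 mg bolus, 30-minute lock): over 30 minutes, 2.5 + 20 = 22.5 mg tramadol; over 60 minutes, 5 + 2 × 20 = 45 mg. This is what the settings permit, not expected use.

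**4. Group size.** Sample size states 16 participants for effect size 1.4, 80% power and alpha 0.05, without saying whether this is per group or in total. A one-sided two-sample t-test reproduces it as 8 per group in two groups (power 0.845). Both 8 and 16 per group are therefore carried below.

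**5. Three-group test if the after reading is used and the device does nothing.** The documents give no VAS SD and no drift, so both are assumptions. With group means 0, d, d, the ANOVA noncentrality is λ = (2/3)·n·d²/SD², on 2 and 3n − 3 degrees of freedom. Example: n = 16, d = 1, SD = 2 gives λ = (2/3)·16/4 = 2.667 and a rejection rate of 0.273.

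| SD | n per group | d = 0.1 | 0.25 | 0.5 | 1.0 |
|---|---|---|---|---|---|
| 1.5 | 8 | 0.052 | 0.060 | 0.091 | 0.231 |
| 1.5 | 16 | 0.053 | 0.071 | 0.143 | 0.455 |
| 2 | 8 | 0.051 | 0.055 | 0.072 | 0.147 |
| 2 | 16 | 0.052 | 0.062 | 0.100 | 0.273 |
| 2.5 | 8 | 0.051 | 0.053 | 0.064 | 0.110 |
| 2.5 | 16 | 0.051 | 0.058 | 0.081 | 0.187 |

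At SD 2, a 10% false-positive rate needs a drift of 0.73 point (n = 8) or 0.50 (n = 16); over SD 1.5-2.5 the range is 0.38-0.92. Kruskal-Wallis on a rounded 1-10 scale (mean 5, SD 2, 6,000 simulations) gives 6-10% at 0.5 point and 13-25% at 1.0.

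**6. Within-group paired t-test.** Noncentrality is √n·d/SD of change, with an assumed SD of change of 1.0-1.5. Over 8-16 patients, a fall not due to stimulation is significant in 5-7% (0.1 point), 13-47% (0.5) or 37-96% (1.0). These are correct rejections of no change; they mislead only if credited to stimulation.

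**7. Upward drift.** Assume further that effect size 1.4 refers to VAS pain with SD 2, so the effect is 1.4 × 2 = 2.8 points. Noncentrality is (2.8 − drift)/2·√(n/2). For a rise of 0, 0.5 or 1.0 point, two-sided two-sample power is 0.969, 0.882, 0.693 (n = 16) or 0.740, 0.572, 0.389 (n = 8).

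**The case against.** The plan never says that after readings will be set against control readings. Its stated aim is the effect of TENS and TAES on pain, not an immediate per-session effect. A natural reading is that the three-group test uses the six shared times, where every before reading matches. From 2 hours on that is a valid randomised comparison of the regimens, including any effect through PCA or rescue use. On that reading there is no clock bias and the only defect is an unnamed reading.

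That stands as far as it goes: a valid comparison survives. But it omits the effect just after a session, which the after readings appear designed to capture, and the text does not commit to it.

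The sizes are also conditional throughout. Drift and SD are assumed, and the 46% corner needs SD 1.5, 16 per group and a full point of drift. The PCA figures are near a ceiling: if the 500 mg total covers 48 hours, the infusion takes 5 × 48 = 240 mg and leaves 260 mg, or 13 boluses, one per about 3.7 hours. PCA is available in every arm, so it is a source of drift and not an imbalance by design. All of this is fair, and it is why no size of bias is claimed.

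Finally, the absence of sham and blinding may threaten the control comparisons more. That is a separate limit, and clock-matching does not require a sham.

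**Conclusion.** The concern holds. On the written schedule, none of the six after readings has a control reading at the same clock time, so the session effect on pain or vital signs, active versus control, cannot be estimated free of elapsed time. This does not depend on any assumed drift or SD; it would change only if controls had a second reading that the text does not list.

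The size and direction of any resulting bias are unknown. It ranges from negligible (drift of 0.25 point or less: 5-6% false positives at SD 2) to material (1.0 point: 15-27% at SD 2, 11-46% over SD 1.5-2.5), and only if the after reading is the one tested. No size is claimed for vital signs.

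Not affected: TENS versus TAES, which share a schedule and can be compared at matched times, and analgesic consumption, which uses the same windows in all groups. This should be fixed, but it does not invalidate the trial.

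**What to change.** **If readings can still be added**

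- Read control pain and vital signs at the same two clock times per session as the stimulated groups.
- State whether the 30 minutes run from the start or the end of stimulation.
- Name the clock-matched after reading as the basis for active-versus-control inference, adjusted for the 30-minute reading taken before the first session. Preoperative pain is an alternative baseline, but Baseline measurements lists it and Preoperative data collection omits it; those sections must first be reconciled.
- Report the within-group before-after tests as descriptive.

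The cost is six extra VAS and vital-sign readings per control patient by the same data collector, plus SAP wording.

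**If data collection is finished**, as the past tense suggests, compare the groups on the before readings at 2, 18, 22, 42 and 46 hours, adjusted for the 30-minute reading. State that this measures carry-over and not the immediate session effect, and label the choice post hoc if it is made after data collection. This costs only wording, but in an open-label trial a post hoc choice carries less weight.

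Neither route removes bias from the lack of sham and blinding: an inert device could still look effective on self-reported pain.

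### Pre-operative PEF and FVC are collected but not used as a covariate when the arms are compared: a possible loss of precision on a secondary outcome, not bias

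*Combined protocol and SAP*

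**What the plan says.** The opening paragraph makes respiratory function a secondary outcome: "Secondary outcome measures were the effects of TENS and TAES use on respiratory functions".

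Baseline measurements lists spirometry among the pre-operative data: "Pulmonary functions (PEF, FVC), vital signs, respiratory rate, saturation and pain level data were also recorded". Preoperative data collection gives the timing: "The characteristics of the patients and ASA classifications, vital signs and respiratory functions were evaluated one day prior to the surgery". The value therefore precedes any stimulation. Pulmonary function tests describes a single procedure: "This process was repeated three times and the best performance was taken as the base value". Postoperative data collection gives the follow-up times: "Respiratory function evaluations of the patients were performed at the 24th and 48th hours".

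For the comparison of arms, Data analysis states "The one-way ANOVA test was used to investigate the difference between the three groups regarding the measured values" for normally distributed values, and "the Kruskal-Wallis test was used for the values that did not comply with a normal distribution". Bonferroni correction is used to locate differences, and Mann-Whitney to compare two groups. No covariate, regression model or between-arm analysis of change is named. Paired tests appear only "when comparing the values of patients in the same group before and after the implementation".

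**The concern.** A baseline measured before treatment, on the same scale as the outcome, is the usual covariate for reducing unexplained variation between patients. The trial collects one for PEF and FVC, and the plan gives it no stated role in comparing the arms. In a small three-arm trial this could make a real difference in lung function harder to detect.

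Two gaps in the text add to this. The plan does not say whether the measured values are post-operative readings or changes from before surgery, so the PEF/FVC contrast under test is undefined. It is also unclear whether pre-operative spirometry enters the paired tests. Postoperative data collection uses before-and-after wording for vital findings and pain around each stimulation session, whereas spirometry follows a different schedule. Even if it does enter them, a test within one arm does not compare arms.

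**Working it through.** **Inputs from the documents.** There are three arms (Randomization). The Sample size paragraph gives sixteen participants, effect size 1.4, 80% power and alpha 0.05. The correlation r is not given. The allocation ratio is not stated either; I assume equal arms.

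**The plan's own figure.** A one-sided two-group t-test with a standardised difference of 1.4 needs 8 per group, 16 in total (power 0.845; 7 per group gives 0.795). A two-sided test needs 10 per group (9 gives 0.796). If sixteen means 16 per group, two-sided power is 0.969, not 0.80. So the figure reproduces only as a two-group total. The text does not say whether sixteen is per arm or in total, so I carry 16 per arm, 8 per arm, and about 16 in total (5 or 6 per arm).

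**ANCOVA against post-operative values alone.** With N patients, three arms and one covariate, the variance ratio for a pairwise contrast is

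(1 − r²) × (N − 4)/(N − 5) = (1 − r²) × (1 + 1/(N − 5)).

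Example, N = 48 and r = 0.5: 0.75 × 44/43 = 0.767.

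**ANCOVA against change scores.** If the pre- and post-operative SDs are equal (an assumption), a change has variance 2(1 − r) relative to the post-operative value. The ratio above is divided by this. Example, N = 48 and r = 0.3: 0.9312/1.4 = 0.665.

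**Detectable difference.** Two-sided noncentral t for one pairwise contrast, 80% power, alpha 0.05/3 = 0.0167, with N − 3 degrees of freedom unadjusted and N − 4 adjusted, in SDs of the post-operative value.

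Triplets are for assumed r = 0.3 / 0.5 / 0.7.

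| Per arm (N) | Variance vs post-only | Variance vs change | Detectable difference, unadjusted → adjusted | Break-even r |
|---|---|---|---|---|
| 16 (48) | 0.93 / 0.77 / 0.52 | 0.67 / 0.77 / 0.87 | 1.18 → 1.14 / 1.04 / 0.85 | 0.16 |
| 8 (24) | 0.96 / 0.79 / 0.54 | 0.68 / 0.79 / 0.89 | 1.74 → 1.71 / 1.55 / 1.28 | 0.24 |
| 6 (18) | 0.98 / 0.81 / 0.55 | 0.70 / 0.81 / 0.92 | 2.070 → 2.065 / 1.875 / 1.546 | 0.29 |
| 5 (15) | 1.00 / 0.83 / 0.56 | 0.72 / 0.83 / 0.94 | 2.331 → 2.363 / 2.145 / 1.769 | 0.34 |

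Break-even r is the correlation above which the detectable difference shrinks relative to the post-only comparison.

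**The non-normal branch.** I compared overall three-arm tests by simulation (20,000 runs per setting, 16 per arm, one arm shifted by an assumed 0.7 SD, r = 0.3 / 0.5 / 0.7):

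- Log-normal data: Kruskal-Wallis has power of about 0.47, ANCOVA on raw values about 0.38 / 0.42 / 0.55, and rank-based ANCOVA about 0.50 / 0.58 / 0.73.
- Normal data: Kruskal-Wallis about 0.46, rank-based ANCOVA about 0.51 / 0.57 / 0.73.

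The type I error of rank-based ANCOVA, simulated at r = 0.5 on normal data with 5 to 16 per arm, was 0.048 to 0.054. On log-normal data it was 0.050 to 0.053.

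**The case against.** The strongest reply is that the plan contains no error here. ANOVA and Kruskal-Wallis are standard and valid in a randomised trial, and adjustment is a choice about efficiency on a secondary outcome. That stands. A reader might infer that the comparison is biased because it ignores baseline; the documents do not support this, because allocation is randomised.

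The second reply is that the gain cannot be fixed from the documents. That also stands. A reader might infer that adjustment always helps, if only slightly. At 5 per arm and r = 0.3 it does not: the detectable difference rises from 2.331 to 2.363 SD.

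Third, replacing both of the plan's tests with raw-value ANCOVA could lose power on skewed data, as the simulation shows at r = 0.3 and 0.5. This is correct, and it is why the change must keep a rank-based branch.

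Fourth, if measured values means changes, baseline already enters the comparison of arms. The post-only figures then do not apply, and the gain shrinks as r rises. The text does not settle this, so both sets of ratios are shown. ANCOVA has the smaller variance in every change-score case in the table.

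A reader might also conclude that pre-operative spirometry is used only in the paired tests. The documents do not show that it enters them at all.

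**Conclusion.** The point holds as a modest opportunity to gain precision on PEF and FVC. It is worth considering, but it does not threaten the validity of the trial. Against post-operative values alone, the variance of a pairwise contrast would fall by about 17 to 23% at r = 0.5 and 44 to 48% at r = 0.7 across 5 to 16 per arm. At r = 0.3 the effect runs from a 7% reduction at 16 per arm to essentially none at 5 per arm, where the lost degree of freedom makes it a slight net loss.

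These sizes rest on an assumed r, equal arms and a linear relation with a common slope. The change-score ratios also assume equal SDs before and after surgery. The point does not reach the primary outcomes, pain and analgesic consumption.

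**What to change.** State which PEF/FVC quantity is compared, and replace the between-arm analysis of these two measures with:

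> PEF and FVC at 24 h and at 48 h will each be compared between arms by ANCOVA, with arm as factor and the patient's own pre-operative value as covariate. Where the plan would use Kruskal-Wallis because the values are not normal, a rank-based ANCOVA (ranks of outcome and covariate) will be used instead. The overall arm test and the three Bonferroni-corrected pairwise contrasts will be taken from the same model.

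The document describes the study in the past tense. If the data have already been analysed, report the adjusted result beside the unadjusted one and label it post hoc.

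No new data are needed. The cost is one error degree of freedom: if r were 0, variance would rise by about 2% at N = 48 (1/43), 5% at N = 24 (1/19), 8% at N = 18 (1/13) and 10% at N = 15 (1/10). The linear, common-slope assumption is hard to check in arms this small. Leave the analyses of pain, analgesic consumption, vital signs and saturation unchanged on this ground.
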